13.6	Study Documents Online and Study Records	19
13.7	Data Management	20
14	Reporting of Results	20
14.1	Investigator.....	20
14.2	Sponsor.....	21
15	Withdrawal of Sponsor	21
16	Overview of Case Report Forms and Questionnaires available online	21

1 Registry Synopsis

Device(s):	All Cochlear devices, eligible for market release.
Study title:	Cochlear - Implanted Recipient Observational Study (Cochlear - IROS).
Participating sites:	Sites selected for voluntary participation in the observational study (Cochlear - IROS), using any Cochlear devices that are eligible for market release.
Study Duration per subject:	Two years follow-up from Baseline registration. Baseline registration online occurs just after the patient is implanted and prior to the first switch-on. Follow-up at 1 and 2 years is recommended to occur in parallel to routine Clinical evaluations. Evaluation at third year post implant follow-up is optional.
Start date	Dec 2011, with ongoing roll out to clinics and countries as languages become available for use. Review of study progress at regular annual intervals.
Number of subjects:	A minimum of 50 recipients per device. Several hundred subjects across device user groups and device configurations are aimed for enrolment in the study /registry.
Study/Registry Design:	
Prospective, longitudinal comparative repeated measures of benefits for implanted hearing impaired subjects, acting as their own intra-subject control, using a selection of subjective evaluation tools provided via an electronic platform for data entry and data collation within a secured environment. Longitudinal repeated evaluations commencing at Baseline (post-implant, pre-switch-on) and repeated annually for up to 3 years post implant.
 
Patient benefits will be compared to safety records for Cochlear devices eligible for market release gathered through post market surveillance. Inter-subgroup (to be classified by device use and configuration) comparisons of performance per assessment tool per interval shall be performed pending numbers of relative data sets.
 
Note: The registry platform is designed to support and sustain uniform data collection on unlimited number of prospectively implanted patients long term.

Evaluation Materials	
Evaluation Tools comprising main measures for study endpoints made available electronically include:
 
 ○ Subjective self- assessment scales (clinically standardised: SSQ and HUI Mk III); ○ Patient profile forms (clinician and recipient questionnaire versions); ○ Hearing threshold measures (routine measures performed at the clinic) ○ Product specific evaluations as required
Inclusion criteria:	
 ○ Post-lingually deafened adults and adolescents who are newly implanted AND prior to first switch-on of their external device. ○ Unilateral, bilateral simultaneous recipients of any implant device(s) available with market approval from the company Cochlear®. ○ Children 10 years or older, and in accordance with local regulations and product labelling. ○ Mentally capable to respond to self-administered assessment scales ○ Willingness to participate and sign the Patient Informed Consent (PIC) form directly or signed by the legal representative. 
NOTE: Unilateral implant-users registered at baseline, electing to opt for a second sequential implant during the course of the 3 year follow-up period shall be re-classified accordingly there-after as sequentially bilaterally implanted.

Exclusion Criteria	
 Individuals excluded from participation in a registry according to national or local regulations. 							
Primary Objectives:	To evaluate longitudinal subjective benefit data using validated standardised questionnaires (HUI Mk3 and SSQ) for prospectively implanted adult and adolescent recipients compared to the preimplant condition. To assess daily use and issues reported through Cochlear's complaints and issues handling procedure.							
Secondary Objectives:	
To provide statistically valid data to support patient management decisions at the clinical, administrative, reimbursement and regulatory levels locally, nationally and internationally.
 
To establish benefits and device functionality for bilateral use over unilateral use for scientific, regulatory and market-oriented communications.
							
Evaluation Plan	Evaluations are performed at the Baseline interval (post-implant and pre-switch-on) with annual follow-up at 1 year, 2 years (and optionally at 3 years) post-implant. Clinicians and recipients are strongly encouraged to use all evaluation tools below.							
			Test interval	Baseline	Follow-up			Comments
	Completed by	Evaluation Tool	Post-implant/ Pre-switch-on	1yr	2yrs	3yrs optional	Baseline & 2 yrs follow-ups desirable	
	Clinician	1. Clinician Questionnaire. (to register the patient)	X	X	X	X	Questionnaire to capture implanted device details, demographics and hearing history.	
	Recipient	2. Implant Recipient Questionnaire	X	X	X	X	Questionnaire to capture patient profile on previous hearing aid use, vocational and educational status	
	Recipient	3. HUI Mark III	X	X	X	X	Standardised General quality of Life measure	
	Recipient	4. SSQ	X	X	X	X	Standardised disease specific Hearing ability measure	
	Clinician	5. Unaided Hearing thresholds	X	X	X		Routine clinical measures at: pre implant; immediately post implant(optional); 1 st yr & 2 nd yr annual reviews	
Clinician	6. Product Specific					As required		
Withdrawal:	
Voluntary withdrawal at any time for any subject at any site.
 
Missing evaluation data at 1 or 2yrs post-implant following registration at Baseline will invalidate longitudinal assessment for the subject concerned.
							
Endpoint:	Changes in self-ratings on each of the self-assessment measures used, at post switch on intervals compared to baseline, per subject, across subgroups/per device-user configuration.							

2 Terms and Abbreviations

Abbreviations	Definition
CI	Cochlear Implant
HUI Mark III	Mark III Health Utility Index
SSQ	Speech Spatial Hearing Qualities questionnaire
EC	Ethics committee
PIC	Patient Informed Consent
RP	Registry Plan
RA	Registry Agreement
EDC	Electronic Data Capture
ISO	International Organisation for Standardization
Patient	Patient = Implant recipient = subject, once enrolled
Clinician	Clinician = Investigator
Cochlear - IROS	Implanted Recipient Observational Study = Registry

3 Introduction

It is important to demonstrate that intervention is clinically efficacious in a real world environment, across large and often diverse populations. Evidence is required to support the product's value proposition for a wide range of industry and non-industry stakeholders: Regulators, Payers, Providers, Patients and Policy Makers, each with a different perspective as to the acceptance and adoption of the intervention.

To address this need, this observational study has been designed to prospectively gather patient-related data for implanted patients including true baseline interval data gathered prior to implant or first activation of the device and subsequent longitudinal follow-up at consistently timed evaluation intervals.

The study will be offered in multiple languages to ensure a wide range and relatively large group of hearing impaired implanted patients across regions representing a range of health service provisions has the potential to serve as a very valuable tool.

Information derived from such this study may be used to complement data obtained through shorter term, smaller scale, controlled clinical trials.

The proposal: To establish a unified approach to assess the benefits from hearing habilitation with the aid of implantable hearing devices in adults and adolescents.

The approach shall include evaluation and collation of patient-related data longitudinally in implanted patients using hearing devices providing either electrical, electro-acoustic or mechanical stimulation in unilateral, bilateral or bimodal configuration.

The information gathered shall be used to help establish the hypothesis that implantable hearing solutions improve the auditory performance and quality of life of implant recipients with a significant hearing impairment. The hypotheses that binaural stimulation is a superior treatment for the habilitation of hearing impairment in affected individuals will also be tested.

In turn this evidence shall be provided to support decisions by clinical professionals and health authorities for provision of unilateral and bilateral implantable devices either on a case by case or as a routine clinical procedure for the treatment of bilateral hearing impairment.

4 Preliminary Investigation and justification

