## INTRODUCTION

This document is a companion document to the Clinical Investigation Plan CEL5277 but does not replace any previous statistical analysis plan: It is to describe the intended method of analysis of data in the adult IROS database with the aim to produce four publications.

It includes a comprehensive description of the recorded sample sizes, the intended statistical analyses with reference to the primary and secondary hypotheses, and additional statistical considerations such as the treatment of missing data.

There is no need to report deviations from this statistical analysis plan in any reports relating from the IROS data source.

The planned analysis for each publication is described in separate sections.

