## 1.2 Study population

All available data will be used for longitudinal and pairwise comparisons.

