### **1.3.3 Analysis Datasets**

#### **1.3.3.1 Intent-to-Treat**

Linear mixed-effects models provide unbiased estimates of effects even in the presence of missing data provided that the data may be assumed to be missing at random. All available data (to the last time point of interest – possibly 2 or 3 years due to limited follow-up beyond that time). The data will be examined for evidence of informed missingness.

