#### **1.3.3.2 Per Protocol dataset**

These are observational, retrospective data and therefore per protocol is not well defined. As above, the data will be examined to determine whether characteristics are different between those who are present or absent at the various follow-up time points.

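### The protocol's rule voiding subjects with a missed year-1 or year-2 visit is not reconciled with the SAP's use of every recorded visit, and it still covers the protocol's own per-device analyses

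*Protocol*

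**What the plan says.** **Protocol.** Section 1 (Registry Synopsis), Withdrawal row: "Missing evaluation data at 1 or 2yrs post-implant following registration at Baseline will invalidate longitudinal assessment for the subject concerned". Section 12.1 plans intra-subject comparisons of SSQ and HUI3 from pre-implant to years 1 and 2, with data on at least 50 recipients of the same device. It does not repeat the Withdrawal rule and gives no other rule for missing visits. It refers to a separate proposal for the analysis methods, which is not among the documents supplied.

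**SAP.** Section 1.2: "All available data will be used for longitudinal and pairwise comparisons". Section 1.3.2.2 fits linear mixed models with a random effect for individual. Section 1.3.3.1 describes these as unbiased "even in the presence of missing data provided that the data may be assumed to be missing at random", and adds: "The data will be examined for evidence of informed missingness". Section 1.3.3.2 says that "the data will be examined to determine whether characteristics are different between those who are present or absent at the various follow-up time points". Section 4.1.1 needs pre/post pairs only, and Section 4.1.2.1 takes year 1 as the post value.

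**Relation between the two.** The SAP Introduction says: "This document is a companion document to the Clinical Investigation Plan CEL5277 but does not replace any previous statistical analysis plan". It limits its aim to four publications and also says: "There is no need to report deviations from this statistical analysis plan". No supplied text withdraws or interprets the synopsis sentence.

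**The concern.** A subject with baseline and year-1 data but no year-2 data is void for longitudinal assessment under one document and analysed under the other. The SAP settles this for its own publications. It does not settle it for the protocol's per-device analyses, which feed the regulatory, reimbursement and marketing uses listed in protocol 14.2. For those, the synopsis sentence is the only stated rule on missing visits.

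Two things are at stake. The first is precision: a valid year-1 change would be discarded because a later visit was missed. The second is possible selection. Protocol 10.4 lists device failure, and a device-related incident with deteriorating health, among the reasons for ending participation. Subjects who leave for these reasons before year 2 would be voided, and such exits are unlikely to be unrelated to benefit. The documents do not say how many there are.

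**Working it through.** **1. The rules side by side**

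| Visits recorded | Protocol synopsis, as written | SAP 1 (mixed model) | SAP 4 (baseline to year 1) |
|---|---|---|---|
| Baseline, year 1, year 2 | used | used | used |
| Baseline, year 1 | void | used | used |
| Baseline, year 2 | void | used | not used |
| Baseline only | void | used | not used |

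The second and third rows are the clearest conflict.

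**2. The plan's own figures.** The SAP's sample sizes (995, 470, 95 and 350) all reproduce exactly as five-group one-way ANOVA calculations at 5% significance and 80% power. The paired t-test in SAP 4.1.2.1 also reproduces: standard error 0.1490534 / 5.9659 = 0.02498, giving a 95% interval of 0.0996 to 0.1985. No arithmetic is in dispute. The protocol's 50 per device cannot be reproduced, because 12.1 gives no effect size, SD or power. Fifty pairs have 80% power for a standardised change of 0.40.

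**3. How many subjects the rule keeps.** The only follow-up figure given is for ZA-01 (SAP 4.1.1): 117 of 161 at year 1.

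- Year-1 retention: 117/161 = 0.727.
- Assumption: year-2 retention among those with year 1 lies between 1.00 and 0.727.
- Kept under a both-visits rule: 0.727 × 1.00 = 0.727, down to 0.727 × 0.727 = 0.528.
- Enrolment for 50 complete subjects: 50/0.727 = 68.8, so 69; 50/0.528 = 94.7, so 95.

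Not all of this loss is due to the rule, since a subject without year-1 data has no year-1 change in any case. The rule's own cost at year 1 is the 117 falling to between 117 and 117 × 0.727 = 85. At the lower end the standard error of the mean year-1 change rises by a factor of 1/√0.727 = 1.17.

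**4. How large a bias could be.** This is a large-sample simulation (2 million subjects). Inputs:

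- HUI3 SDs of 0.188 before and 0.168 after (SAP 1.3.1, Table 2).
- Pre/post correlation (0.188² + 0.168² − 0.182²) / (2 × 0.188 × 0.168) = 0.48.
- True gain 0.149 (SAP 4.1.2.1).
- Assumed: normal scores, the same gain at both years, year-1 to year-2 correlation 0.7, and 72.7% retention at each step.

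In the first two dependent scenarios only year-2 retention depends on the score; in the third, retention at both years does. Higher values are assumed more likely to stay; the opposite dependence would reverse the signs. Entries are the bias in completers' mean gain at year 1 / year 2, by odds ratio of retention per SD.

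| Retention depends on | 1.4 | 2.0 | 3.0 |
|---|---|---|---|
| Nothing (odds ratio 1) | 0.000 / 0.000 | – | – |
| Year-1 score | +0.007 / +0.002 | +0.014 / +0.005 | +0.019 / +0.007 |
| Year-1 change | +0.017 / +0.013 | +0.032 / +0.024 | +0.045 / +0.034 |
| Baseline score | −0.020 / −0.020 | −0.035 / −0.035 | −0.046 / −0.046 |

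Maximum likelihood on all visits had a bias of about 0.000 throughout. That is expected, because each scenario is missing at random by construction and the calculation left the covariance unrestricted. For scale, SAP 1.3.1 puts the minimum clinically important HUI3 change at 0.03.

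**The case against.** The rule is one line in a synopsis row, and the protocol's statistics section does not repeat it. It can be read narrowly, as saying only that the subject lacks a full trajectory. Other protocol text favours that reading: 6.2.1 makes the intra-subject comparison for all implanted patients, the synopsis design plans comparisons by interval, and Section 5 tests bilateral against unilateral implantation at the first year. SAP Section 1 already plans checks on missingness and tables by subsequent attendance (1.3.3 to 1.3.4.1, 1.3.7). The two documents also ask different questions: change from baseline by device in the protocol, and an age-group-by-visit interaction in SAP Section 1. Differing results would not by themselves show a missing-data conflict.

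Much of this stands, and it rules out several stronger readings.

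- *The SAP keeps the protocol rule in force.* A reader might infer this from "does not replace any previous statistical analysis plan". That clause concerns earlier statistical analysis plans, not the protocol. The gap is one of silence.
- *The planned publications are completers-only.* They are not; no SAP analysis applies the both-visits rule. Section 4 does use year-1 pairs and states no missing-data handling of its own.
- *The rule is biased.* Bias depends on why visits are missing, and the documents give no data on that. Complete cases can also be unbiased when missingness depends only on covariates in a correctly specified model.
- *The best-followed centre has lost 27%.* The count is a December 2019 snapshot, and some of the 44 without year-1 data may not have been due.
- *Follow-up elsewhere is worse.* SAP 4.1.1 singles out ZA-01 for good follow-up but gives no rate for any other centre.

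The narrow reading does not remove the point. Longitudinal assessment is not defined, and the plain wording voids it when either visit is missing.

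**Conclusion.** The conflict is real and rests on exact text. The protocol's synopsis rule and the SAP's approach treat subjects with a missed year-1 or year-2 visit differently, and nothing supplied says which governs. The exposure lies in the protocol's per-device analyses and the reports drawn from them, not in the SAP's publications.

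Read as written, the rule discards usable visits. If ZA-01's 73% is taken as year-1 retention and year-2 retention lies between 100% and 73%, about 73% to 53% of subjects remain. The part due to the rule at year 1 is between none and 32 of the 117 (117 − 85). Bias is possible but not shown. Under the assumed mechanisms it ran from zero to about 0.046 HUI3 units in absolute size, passing 0.03 only at odds ratios of about 2 or more per SD. The all-visits model is safer only so far as missing at random is credible, which is why the SAP's planned checks matter. The sentence should be changed.

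**What to change.** Replace the synopsis sentence with: *All available visits from all registered subjects are used in the longitudinal mixed-model analysis; subjects with both year-1 and year-2 data form a sensitivity set only.*

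Require a baseline plus a follow-up value only for change-score summaries, and only at the visit being summarised. Do not make baseline plus at least one follow-up a condition of entry to the mixed model. That would be narrower than SAP 1.2 and would drop subjects with a baseline alone, or without a baseline, whom the model can use.

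State in the SAP that this rule governs over the synopsis sentence. The cost is wording in the two documents; no new data, visits or sample-size change are needed.

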4.1 Preclinical testing

No preclinical testing is required for enrolment of an implanted subject into the registry outside of routine clinical practice.

5 Study Objectives

- To evaluate longitudinal subjective benefit data using validated standardised questionnaires (HUI Mark III and SSQ) for prospectively implanted adult and adolescents using unilateral; bilateral or bimodal configurations of device types.
- To provide statistically valid data to support patient management decisions at the clinical, administrative, reimbursement and regulatory levels locally, nationally and internationally.
- To establish benefits and device functionality for bilateral use over unilateral use for scientific, regulatory and market oriented communications

The hypotheses:

The information gathered shall be used to test the primary hypotheses that implantable hearing solutions improve **the auditory performance** of implant recipients compared to their preimplant condition.

Reported benefits evaluated at 1 year postimplant will remain stable at 2nd and 3rd year postimplant compared to the Baseline evaluation of the preimplant condition.

Severe to profound bilaterally impaired adults and adolescents undergoing bilateral implantation will report a higher level of benefits post implant on self-reported scales, the SSQ and HUI Mark III, compared to those reported by comparable groups of patients implanted unilaterally at the first year follow-up.

Participation in the observational study presents no additional risk to the patient as they are implanted with market released devices and there is no additional burden to the subjects beyond clinical followup.

6 Study Design and End-points

The clinical investigation is designed as a prospective repeated measures longitudinal study with intra-subject controls and inter-group comparisons for device type and configurations across multiple implant

centres cross-culturally using a selection of evaluation tools including clinically standard self-assessment scales, threshold measures, product specific and non-standardised questionnaires for the clinician and implant recipient made available through the electronic platform. Participating clinics are encouraged to collect data as per the evaluation plan outlined. Evaluation tools are provided via the electronic platform.

The registry is aimed at collection of data for patients who have already made the decision together with their implant centre clinician for an implant device from the company Cochlear®.

Participating in the observational study for each clinic and patient is voluntary. Both the clinic and patient are free to electively remove themselves from participation in the registry at any time. Patients should be enrolled that meet the selection criteria without bias This will enable interpretation of the results and application for the implant population at large.

Clinics are asked to enrol newly implanted patients into the study in chronological order of implantation.

Enrolment should occur after implant and must be prior to the first switch-on of their implanted device.

- **All prospective implantees who are able to provide consent for their participation in the observational study or for whom consent is provided by their legal representative.**
- All prospective implantees awaiting their first switch on of their external device
- Children 10 years or older and in accordance with local regulations and product labelling.
- Implantees or carers who are physically and mentally-able to complete the questionnaires independently as self-administered and *not as an interview* are able to participate.
- Each patient is evaluated at or immediately prior to the first switch on to obtain **baseline responses related** to their hearing experiences and perception of quality of life in **their pre-implant hearing condition**. Standard clinical tools: the SSQ and HUI Mark III are available for use and non-standard questionnaires for Clinicians and Patients
- Each patient is to be followed up through routine clinical procedures and in parallel asked to complete the post-implant versions of the questionnaires at their 1st, 2nd and 3rd year(optional) follow-up appointment \pm 2 months of the expected time frame.
- Inter-group comparisons of outcome data require a minimum of 100 subjects per subgroup per device type and configuration (and of comparable age group) for data analysis and formal report of their HUI Mark III data at the 1st, 2nd and 3rd year (optional) post-implant compared to their preoperative baseline responses. Statistical comparisons will be made in accordance with the recommended analytical procedures as validated by HUI Inc, the developers of the questionnaires.
- Inter-group comparisons of outcome data require ideally a minimum of 50-100 subjects per subgroup per device type and configuration (and of comparable age group) for data analysis and formal report of their SSQ data at the 1st, 2nd and 3rd year post-implant compared to their preoperative baseline responses. Analysis will performed via comparison of mean responses per subcategory scale of questions of the SSQ as proposed by the developers. Sub scale category scores will be compared across time both intra-subject and inter-subject using parametric tests of comparison.
- Data gathered from the general questionnaires will be collated to provide a descriptive report of patient characteristics of the enrolled population.

- Hearing threshold data for pure-tone stimuli under headphones for air-conduction and via a bone conductor for bone-conduction may also be recorded by the clinician following routine measurements at the clinic at the 1st, 2nd and 3rd year post-implant compared to their preoperative baseline responses. Test data collected at one additional time interval post-implant immediately post-surgery and prior to switch-on may also be entered and collated. Threshold data specifically for air-conduction measures per frequency per subject will be compared to determine the changes in threshold over time for each ear. Changes of +/-5 dB will be considered clinically insignificant. Changes in thresholds per frequency will be reported intra-subject and for inter-subject groups.
- Other evaluation measures such as speech audiometry are not specified for longitudinal data collection by the protocol. However additional clinic specific data may be recorded by each clinic on the hearing threshold summary forms provided for the same group of subjects for both formal internal and external reports.
- Participating clinics and or patients wishing to complete the questionnaires online will be required to confirm the minimum technical PC requirements and firewall conditions. (See Section 13).
- Product-specific measures (e.g. surgical experience, in situ thresholds).

